**Histologic and genomic assessment of skin biopsy specimen:**

Each biopsy specimen will be bisected. Half will be formalin fixed and sent for histologic evaluation. Histologic assessment will be performed by an experienced academic dermatopathologist, who will be blinded to the study design. This will be performed within the Duke Dermatology Skin Disease Research Center (SDRC).

Dermal thickness will be measured and compared before and at the end of treatment.

The other half will undergo processing for Nanostring gene expression analysis. Specimens will be sent to the Nanostring Core Facility at the University of North Carolina (UNC) , de-identified except for study subject number. Gene expression analysis is included for future research purposes only. A Material Transfer Agreement will be completed and executed between Duke and UNC. MTA will be fully executed and uploaded into eIRB prior to any samples being sent outside of Duke.

The Lineberger Cancer Center Translational Genomics Laboratory (TGL) at UNC provides an assortment of analysis services employing the Nanostring™ nCounter platform. These include gene expression, miRNA expression and miRNA gene expression copy number variation analysis, single gene expression, lncRNA expression, Chip-String and RNA-Protein profiling. Nanostring™ supplies custom and off-the-shelf assays for various groups of target genes including immunology, inflammation, and pan cancer panels offering pathway, immune and progression profiling. TGL maintains 2 nCounter Prep Stations which can process 12 post-hybridization samples every 3 hours. A generation 2 nCounter digital analyzer can sequentially scan up to 6 cartridges of 12 samples each with a maximum resolution scan requiring approximately 5 hours per

[figure not shown]
cartridge. Data is provided to the client electronically for analysis using the NSolver v. 3.0 software provided by Nanostring™. LCCC Bioinformatics can also provide Nano Nanostring™ string analysis services. TGL employs 4 trained specialists experienced in assorted types of Nanostring™ assays.

All sample information and metrics are recorded and maintained in the gPATH Lab Information Management System (LIMS) designed and maintained by LCCC Bioinformatics.

To distinguish gene expression profiles in a sample enriched for keratinocytes, the epidermis and dermis will be separated using a previously described protocol that allows for high quality RNA extraction. Total RNA will be isolated from epidermal and dermal portions of each biopsy specimen. RNA will be hybridized to a custom made kit based on the nCounter Human Kinase Gene Expression Code Kit (which includes 519 color-coded human kinase genes) with additional genes that screen for innate and adaptive immune response. After washing and cleaning, the sample cartridges will be read in the nCounter SPRINT analyzer which allows automated data collection for up to 24 samples in one day.

Skin sections from the unaffected individuals will be used as control. These are obtained from an IRB exempt protocol that allows us to utilize normal skin from unidentified, healthy donors (Pro00012656, Access to anonymous and de-identified samples).

Genes that show more than 3-fold differences between lesional and non-lesional or normal skin, and between baseline and at 12 weeks, will be analyzed using gene function-based analysis tools such as GeneSpring, and grouped into the categories of cell signaling, structure, cell cycle, survival, and inflammation, as described in our previous studies.

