**4. Design & Procedures:**

A Phase 2, pilot, proof-of-concept, open label, single arm prospective study to assess the safety, tolerability and efficacy of using crisaborole 2% ointment for adult morphea. We will recruit 20 adult ( $\geq 18$  years of age) patients with morphea.

Patients will be recruited from the Duke University Dermatology Autoimmune Disease Clinic. In addition, patients will also be recruited from the entire Duke System, and from community and academic dermatology practices.

Patients will be identified by their physician, nurse, or other member of their clinical care team. Upon notification by the primary team, the study team will approach patients to discuss the study, treatment protocol, associated procedures and obtain informed consent. Patients who are referred from outside of Duke will have to obtain a Duke Medical Record Number (MRN).

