**Skin punch biopsy of sentinel plaque:**

A sentinel plaque will be selected at baseline. A 4 mm skin punch biopsy will be performed at baseline and at 12 weeks, on the same affected plaque.

If a biopsy has been previously taken of the affected plaque and is available for review, this will be used as the baseline biopsy. Patients who drop out of the study because of progression of their disease or adverse effects will undergo a skin punch biopsy at the time of drop out.

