## Summary of Clinical Trial Design

	Baseline	Week 4	Week 8	Week 12	Week 16	Week 20
Crisaborole 2% ointment twice daily	x	x	x	x		
Clinic visit	x	x	x	x		x
LoSCAT scoring	x	x	x	x		x
DIET scoring	x	x	x	x		x
Skin punch biopsy	x			x		
Urine HCG	x	x	x	x		
Skindex 29	x	x	x	x		x
Skin imaging (ultrasound)	x	x	x	x		x
Photography	x			x		x

**Primary outcome measure** is the change in dermal thickness on skin biopsy at 12 weeks.

**Secondary outcome measures** are the following:

- Change in DIET score of sentinel plaque at 4, 8 and 12 weeks.

- Change in LoSCAT score at 4, 8 and 12 weeks.
- Skindex-29 at 4, 8 and 12 weeks.
- Change in dermal thickness of sentinel plaque by ultrasonography at 4, 8 and 12 weeks

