**12. Data Analysis & Statistical Considerations:**

We will aim to recruit 20 patients in the study. We anticipate to see a 30% decrease in dermal thickness at 12 weeks compared to baseline, using histologic evaluation of skin punch biopsy specimens. Using measurements of dermal thickness that we obtained from our archived morphea skin biopsies, we estimated that we need 11 patients to detect 30% change in dermal thickness with a power of 0.80 and an alpha of 0.05. The goal to recruit 20 patients allows for possible drop-outs, while still allowing us to perform statistically significant analysis.

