#### References

Women and minority volunteers will be encouraged to enroll, but no formal subgroup accrual goals are planned.

The descriptions and grading scales found in the revised NCI Common Terminology Criteria for Adverse Events (CTCAE) version 4.0 will be utilized for AE reporting.

Months 1-6	Months 7-12	Months 13-18	Months 19-24
Subject recruitment (1-2 patients per month), clinical and objective assessment, collection of biopsies			Genomic profiling, data interpretation and analysis, and paper writing.

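### The histology reader for the primary outcome is masked to the study design but not to biopsy time point, so a before-after reading shift is not excluded

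*Combined protocol and SAP*

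**What the plan says.** Section 4 of the combined protocol and SAP describes an "open label, single arm prospective study to assess the safety, tolerability and efficacy". The primary outcome, under Summary of Clinical Trial Design, "is the change in dermal thickness on skin biopsy at 12 weeks".

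The subsection on histologic and genomic assessment has the only masking statement for this outcome: "Histologic assessment will be performed by an experienced academic dermatopathologist, who will be blinded to the study design". On the measurement itself it says only: "Dermal thickness will be measured and compared before and at the end of treatment".

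Two other passages deal with coding. The same subsection de-identifies, apart from a study number, the half-specimen sent out for gene expression. Section 13 replaces history numbers with study numbers for data handling and analysis. The subsection on the skin punch biopsy adds that "If a biopsy has been previously taken of the affected plaque and is available for review, this will be used as the baseline biopsy".

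**The concern.** With no control arm, the primary analysis compares end-of-treatment slides with baseline slides and nothing else. The masking that protects this comparison is masking to time point, and the plan does not state it. A reader could be told nothing about the design and still see the order of two slides from a date, a label or an accession number. The two coding rules hide who the patient is, not when the tissue was taken, and neither is stated to cover the histology slides.

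If end-of-treatment slides were read systematically thinner, the shift would add to any apparent drug effect. If they were read systematically thicker, it would hide a real one. No second arm is read in the same way to cancel it.

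**Working it through.** **1. The plan's own figure.** Section 12 states that "we estimated that we need 11 patients to detect 30% change in dermal thickness with a power of 0.80 and an alpha of 0.05". Its table gives power 0.80310 for a two-sided paired Wilcoxon test at N = 11 and effect size 1.000. Take the effective sample size as N × 3/π rounded down: 11 × 3/π = 10.50, so 10. A noncentral t with 9 degrees of freedom and noncentrality 1.000 × √10 = 3.162 then gives power 0.80310. The figure is reproduced, and the sample size is not in dispute.

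**2. The SD of the change (assumption).** Effect size = mean change / SD. If the 30% change in the text belongs to the N = 11, effect-size-1.000 row, SD = 30% / 1.000 = 30% of baseline. The table gives no unit, so this link is assumed. SDs of 20% and 40% are also shown.

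**3. What a reading shift would do.** Suppose the drug has no effect and the change in pair *i* is D_i = b + e_i, where b is the reading shift and e_i is normal with mean 0 and the SD above. The test is the exact two-sided signed-rank test at 5%. Its exact size is 4.84% with 20 pairs and 4.20% with 11. The documents give no value of b; 2%, 5% and 10% of baseline are assumed. At SD 30% they equal 0.02/0.30 = 0.067, 0.05/0.30 = 0.167 and 0.10/0.30 = 0.333 SD. Each cell with a shift comes from 400,000 simulations.

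| False-positive rate, all pairs shifted | no shift | 2% | 5% | 10% |
|---|---|---|---|---|
| 20 pairs, SD 30% | 4.8% | 5.7% | 10% | 28% |
| 11 pairs, SD 30% | 4.2% | 4.6% | 7% | 15% |
| 20 pairs, SD 20% | 4.8% | 6.8% | 18% | 54% |
| 20 pairs, SD 40% | 4.8% | 5.3% | 8% | 18% |

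If only 5 of 20 pairs shift by 5% or 10% (SD 30%), the rates are 5.1% and 6.0%. With 10 of 20 they are 6.2% and 9.9%.

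In the other direction, take a true 30% fall, SD 30%, and a shift toward thicker end-of-treatment readings of 0, 2%, 5% or 10%. Power is 98.5%, 97%, 93% and 79% with 20 pairs, and 81%, 75%, 65% and 47% with 11.

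**4. How large a shift steady drift could give.** The plan neither states nor rules out reading slides as they arrive. The timetable in section 12 has "Subject recruitment (1-2 patients per month), clinical and objective assessment, collection of biopsies". Twenty patients at 2 or 1 per month take 20/2 = 10 or 20/1 = 20 months. Adding 12 weeks (about 2.76 months) puts the last week-12 biopsy at about month 13 or 23. Baseline and week-12 slides then interleave, and each pair carries only 12 weeks of drift:

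- A 5% shift in every pair needs cumulative drift of 5% × 13/2.76 = 24% to 5% × 23/2.76 = 42% of thickness over the study.
- A 10% shift needs 47% to 83%.
- Conversely, an assumed cumulative drift of 10% gives each pair 10% × 2.76/23 = 1.2% to 10% × 2.76/13 = 2.1%. With 20 pairs at SD 30% the false-positive rate then lies between about 5% and 6%.

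Steady drift therefore explains about the 2% column. The 5% and 10% columns need another cause, namely a reader whose knowledge of time point influences most readings.

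**The case against.** The strongest reply is that the stated masking already blocks the main route to a large shift. A reader who does not know that this is a before-after treatment study does not know that thinning is hoped for, and a slide labelled as baseline would itself give the design away. On that view the sentence is loosely worded and masking is not absent. Much of this stands: the protection against expectation is real, and calling the reading unmasked would be wrong. But it is partial, because dates or accession numbers can still show order, and nothing in the text prevents that.

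The second reply is the drift arithmetic above, and it stands. An abrupt change in reading would affect only the pairs that straddle it.

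Third, a reader might infer that a histology shift could never be told apart from a drug effect. The documents do not support that. Section 4 also measures dermal thickness of the sentinel plaque by ultrasound at baseline and weeks 4, 8 and 12, independently of the histology reading. A change seen only on histology would be a warning. Ultrasound is a secondary outcome with no masking statement of its own, so the check is partial.

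**Conclusion.** The point holds in a limited form. The reader of the sole primary outcome is masked to the design but not to the one factor being compared, and a shift tied to time point is not excluded. The documents do not show that a shift will occur or how large it would be.

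A reader might take the 28% as the expected false-positive rate. It is not. It requires a 10% shift in all 20 pairs and an SD of 30%, both assumed, and steady drift would not plausibly produce such a shift. A shift of about 2%, or one confined to a quarter of the pairs, has little effect. It becomes material at about 5% or more in most pairs.

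A reader might also infer that archived baselines call for a separate sensitivity analysis. With a quarter of pairs shifted, the false-positive rate barely moves, so a stated limitation is enough. Masking to time point does not supply the missing control arm or remove natural-course change. It removes one avoidable source of shift at little cost.

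**What to change.** Replace the masking sentence in section 4 (histologic and genomic assessment) with:

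> The dermatopathologist will be masked to study design, patient and biopsy time point. Slides carry a random code assigned by existing study staff other than the reader. Both slides of a patient are measured by the same reader in the same session, in random order among other patients' slides. The key is released after the measurements are locked.

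Report as a limitation that masking may be incomplete where an archived biopsy serves as baseline.

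The cost is minor coding work. There is no extra biopsy or visit, and the same reader is used. The downside is that a baseline slide is not measured until the patient's end-of-treatment slide is available. A single batch at the end of the study is not required. At one patient per month it could not start until about month 23, leaving little of the months 19-24 set aside for "Genomic profiling, data interpretation and analysis, and paper writing". Sessions that hold complete pairs from several patients avoid that wait for all but the last patients.

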#### **Retention of data and samples for future research:**

With subject agreement, subject samples and data obtained during this research study will be retained for future research under previously established bio and data repositories. This retention of samples will require separate subject consent to Pro00006230 and Pro00006313.

#### **Clinical assessment**

Patients will have a clinical assessment at baseline and at weeks 4, 8 and 12. After week 12, patients who need further treatment will undergo standard of care treatment as determined by their primary dermatologist. An optional post treatment follow-up will be performed at week 20.

Physician and patient reported assessment and skin imaging will be performed at baseline, week 4, 8 and 12, and at week 20. Photography will also be performed at baseline and week 12.

Physician assessment will utilize two previously described and validated scoring metrics. The sentinel plaque will be evaluated using Dyspigmentation, Induration, Erythema, and Telangiectasias (DIET) score. Overall disease severity will be evaluated using the Localized Scleroderma Cutaneous Assessment Tool (LoSCAT).

Health-related quality of life (HRQOL) will be measured using Skindex-29 which has previously been applied to morphea, and has a pruritus component.

Photographs will be taken using a standardized clinic camera.

B-Mode ultrasonographic imaging will be utilized to measure dermal thickness of the sentinel plaque at baseline, week 4, 8 and 12 and post-treatment at week 20.

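### No masking to visit is described for the ultrasound dermal-thickness secondary outcome, in an open-label single-arm trial where a reading shift would enter the change directly

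*Combined protocol and SAP*

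**What the plan says.** Section 4 (Design & Procedures) describes "A Phase 2, pilot, proof-of-concept, open label, single arm prospective study". Under Clinical assessment, "B-Mode ultrasonographic imaging will be utilized to measure dermal thickness of the sentinel plaque" at baseline and at weeks 4, 8 and 12, with a further scan at the optional week 20 visit. The Summary of Clinical Trial Design lists as a secondary outcome "Change in dermal thickness of sentinel plaque by ultrasonography at 4, 8 and 12 weeks". The primary outcome is a different measurement of the same quantity: it "is the change in dermal thickness on skin biopsy at 12 weeks".

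Blinding is mentioned once, for the dermatopathologist assessing the biopsies, "who will be blinded to the study design". For ultrasound the documents do not say who acquires or reads the scans, whether the reader knows the visit or the earlier values, whether images are kept, or in what order they are measured. Section 12 gives no analysis for ultrasound.

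**The concern.** Every patient is treated, so whoever knows the visit also knows the length of exposure. Section 12 anticipates a 30% fall in histologic thickness by week 12, so the study team has a stated expectation of thinning. In a controlled trial, a reader's tendency to measure later scans as thinner would largely cancel between arms if the reader did not know the arm. Here nothing cancels it, and the whole shift becomes part of the estimated change.

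Ultrasound is also the only repeated instrumental measure. The other repeated secondary outcomes are two physician scores (DIET and LoSCAT) and a patient questionnaire (Skindex-29). It is the natural corroboration of a primary outcome that rests on two biopsies per patient, the first of which may be an earlier one already on file. Its value as corroboration depends on its readings not being influenced by knowledge of the visit. Unlike an induration score, a saved image can be measured later without that knowledge.

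**Working it through.** **1. The plan's own figure.** The only power calculation concerns histology: 0.80310 at N = 11, effect size 1.000, two-sided alpha 0.05, paired Wilcoxon test. Deflating N by the Wilcoxon efficiency for normal data gives 11 × 3/π = 10.50, rounded down to 10. A two-sided paired noncentral-t calculation with n = 10 and effect size 1.0 gives power 0.8031, which reproduces the figure. It has no bearing on ultrasound, and masked reading would change neither it nor N nor alpha.

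**2. Which thickness readings are protected.**

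| Measurement | Role | Blinding described |
|---|---|---|
| Dermal thickness, biopsy | Primary | Dermatopathologist, blinded to the study design |
| Dermal thickness, ultrasound | Secondary, repeated | None |

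**3. Illustration of size.** The documents give no reader-bias figure, so these inputs are assumptions:
- systematic shift δ between baseline and a later reading: 2%, 5% or 10% of thickness
- SD of change σ: 20% to 30%. The upper value has a loose anchor in histology: a 30% change at effect size 1.000 implies σ = 30%/1.000 = 30%. Nothing comparable exists for ultrasound.
- n = 20 (planned enrolment) and n = 11 (the number Section 12 requires)
- no true change

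No test is specified for ultrasound, so I used a two-sided 5% paired t-test and counted rejections in the favourable direction only (nominal 2.5%):

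P = 1 − F(t₀.₉₇₅,ₙ₋₁; df = n − 1, noncentrality = (δ/σ)√n)

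where F is the noncentral t distribution function. Worked case: δ = 5%, σ = 20%, n = 20. Then δ/σ = 0.25, noncentrality = 0.25 × √20 = 1.118, critical value 2.093, P = 0.185.

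| Assumed shift | δ/σ (σ = 30% to 20%) | P at n = 20 | P at n = 11 |
|---|---|---|---|
| 2% | 0.067 to 0.10 | 0.047 to 0.062 | 0.039 to 0.049 |
| 5% | 0.167 to 0.25 | 0.105 to 0.185 | 0.072 to 0.114 |
| 10% | 0.333 to 0.50 | 0.293 to 0.564 | 0.169 to 0.323 |

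Replacing n = 20 by 20 × 3/π = 19.10, rounded down to 19, to mimic a Wilcoxon test gives about 0.10 to 0.18 for a 5% shift and 0.28 to 0.54 for 10%. The choice of test matters little.

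**4. Reading load.** 20 patients × 4 visits = 80 scans; with the optional week 20 visit, at most 20 × 5 = 100. The timeline in Section 12 places data interpretation and analysis in months 19-24, so a deferred reading fits.

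**The case against.** The strongest reply is that the documents are silent on masking; they do not plan an unmasked reading. A reader might infer that thickness is measured at the visit, by staff who know the visit, with hand-placed borders. That is plausible for B-mode imaging, but none of it is stated, and neither is image storage. The supportable claim is that masking is not described.

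Four further points have weight:
- **The sizes rest on assumption.** A 2% shift barely moves the error rate. A 10% shift is a third of the 30% effect anticipated for histology (10/30), which is not small. The n = 20 figures also assume no drop-out. This stands, and it is why the table shows the small shift and n = 11.
- **The remedy is partial.** Coded reading masks the measurement step. Probe placement, pressure and choice of frame stay with an operator who knows the visit. A reader who also acquired the scans may recognise some, and a scar from the 4 mm baseline punch could identify a later image.
- **The effort is not nil.** It is tempting to say that masked reading needs no extra staff and costs nothing. The documents describe no imaging staff, so this cannot be checked, and up to 100 scans must be coded and read.
- **This is a 20-patient pilot.** The primary outcome is histologic, with a reader described as blinded. Masked ultrasound reading would not remove the causal limits of a before-after comparison.

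These points limit the claim but do not remove it. The plan protects one reading of dermal thickness and describes no protection for the other, and a simple improvement is available.

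**Conclusion.** The point holds in a limited form. No masking to visit is described for a named secondary outcome in an open-label single-arm trial, and any reading shift driven by expectation would enter the within-patient change uncancelled. If such a shift existed, the chance of a spurious significant benefit could range from about 4-5% (2% shift, n = 11) to 29-56% (10% shift, n = 20), against 2.5% nominal. These figures are illustrative: the shift and the SD of change are assumed, and the test is my choice.

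A reader might go further and conclude that the ultrasound result will be biased, or that the trial's main conclusion is at risk. The documents support neither. They do not show that a shift will occur, and the primary endpoint, its power calculation and the sample size are unaffected. The change is worth making before the scans are read, as an improvement to one of four secondary outcomes.

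**What to change.** In Section 4, Clinical assessment, add that:
- all ultrasound images are saved, with an image-quality check at the visit while the scan can still be repeated;
- images are framed away from the biopsy site where possible, so that a scar does not reveal the visit;
- after the last patient's last visit, patient, date and visit labels are removed, and one existing staff member measures all images in random order;
- these readings, and no others, are used for the ultrasound secondary outcome.

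**Cost:** the time to code and read 80 images, or up to 100 with week 20. No patient, visit, procedure, endpoint, alpha or sample size changes.

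**Downsides:** a poor image missed at the visit cannot be repeated later, and acquisition remains unmasked. The report should say that only the measurement step was masked.
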